# 9.8 Safety and tolerability endpoints

The safety set is used to perform all safety analyses. Baseline is defined as the last value prior to dosing. Change from baseline will be calculated for all continuous safety parameters.

# 9.8.1 Adverse events

The AE coding dictionary for this study will be Medical Dictionary for Regulatory Activities (MedDRA). It will be used to summarize AEs by primary system organ class (SOC) and preferred term (PT). All adverse events will be displayed in listings. A treatment-emergent adverse event (TEAE) is defined as an adverse event observed after starting administration of the specific treatment, and up to 5 days (120 hours) after study drug administration. If a subject experiences an event both prior to and after starting administration of a treatment, the event will be considered a TEAE (of the treatment) only if it has worsened in severity (i.e., it is reported with a new start date) after starting administration of the specific treatment, and prior to the start of another treatment, if any. All TEAEs collected during the investigational period will be summarized.

The number of subjects with treatment emergent AEs will be summarized by:

- 1. treatment, MedDRA SOC and PT;
- 2. treatment, MedDRA SOC, PT and severity;
- 3. treatment, MedDRA SOC, PT and drug relatedness.

#### 9.9 Pharmacokinetic and pharmacodynamic endpoints

#### 9.9.1 Pharmacokinetics

The individual plasma and saliva drug concentrations will be listed by treatment, subject, visit and time. Individual plasma and saliva drug concentrations versus time will be plotted in panel plots for each treatment using both a linear and log y-axis.

The individual plasma and saliva drug concentrations will be summarised (n, mean, SD, %CV, median, Min and Max values) by treatment and time, and will also be presented graphically as mean over time, with standard deviation as error bars.

When an actual sampling time of a drug concentration sample differs from the protocol time by more than 20% and at least 10 minutes the concentration will be excluded from calculation of descriptive statistics and a note will be added to the sample in the listing.

The individual PK parameters (except  $t_{max}$  and  $t_{lag}$ ) will be summarized (n, mean, SD, %CV, geometric mean, geometric %CV, median, Min and Max) and will be presented graphically as boxplots. For  $t_{max}$  and  $t_{lag}$ , the n, median, Min and Max statistics will be reported.

During part A, linear correlations will be assessed between saliva and plasma concentrations of clonazepam. When a linear correlation is found, the resulting formula will be used to estimate plasma concentrations in part B of the study. When there is no linear correlation, a population pharmacokinetic model of plasma and saliva concentrations will be constructed using nonlinear mixed effects modelling via NONMEM. Based on the PK model of plasma clonazepam concentrations in plasma, linear and/or exponential relationships will be explored to predict salivary clonazepam. Exploratory analysis of covariates will be performed on the models concerning the relationships between salivary and plasma clonazepam. The resulting optimal model will then be used to predict plasma concentrations from saliva concentrations in part B of the study.

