#### Sample Size Justification and statistical methodology

For part A, Linear and non-linear relationships between plasma and saliva concentrations will be explored. In the case of a nonlinear relationship, which could be expected due to delayed penetration in the salivary compartment, it is widely accepted that around 20 subjects are necessary to develop a reliable model. The predictive capability of the two regression equations will be compared to determine which method is superior.

For part B, the sample size is based on practical considerations (the total ARID1B population in the Netherlands) and based on the previous study (CHDR1828). We consider 20 patients to be a feasible amount of subjects to recruit, while obtaining sufficient power to detect clinically relevant treatment effects. To establish treatment effects the repeatedly measured cross-over PD endpoints will be analyzed by mixed model analyses of variance with treatment, period, time, and treatment by time as fixed effects, with subject, subject by treatment and subject by time as random effect, and with the (average) baseline value as covariate. The PK-PD relationship between clonazepam concentration and PD endpoints will be assessed by calculating the estimated plasma concentration using the derived formula in part A of the study.

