## 2 STUDY OBJECTIVES

- To test the hypothesis that clonazepam administration has acute beneficial effects compared to placebo on neurocognitive tests.
- To test the hypothesis that multiple-doses clonazepam has beneficial effects compared to placebo on behaviour and cognitive function in ARID1B patients as measured by the ABC, and CGI-I scale.
- Assess safety and tolerability of clonazepam in ARID1B patients.
- To assess the potential of at-home neurocognitive tests for the evaluation of treatment effects in children with neurodevelopmental disorders.
- To assess and compare the difference in predictive capability between linear and nonlinear (NONMEM) regression of the saliva:plasma relationship.

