## 6.2 Pharmacokinetic endpoints

Part A: serum and saliva. Part B: saliva only.

- The maximum serum concentration, Cmax
- $\circ$   $\;$  The time to reach maximum serum concentration, tmax  $\;$
- $\circ~$  The terminal disposition rate constant (\lambdaz) with the respective half-life, t1/2  $\,$
- The area under the serum concentration-time curve from zero to infinity, AUC0-inf
- The area under the serum concentration-time curve from zero to t of the last measured concentration above the limit of quantification, AUC0-last
- o Clearance, Cl
- Volume of distribution, Vz

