### 9.9.4 PK/PD modelling

Population PK and PK/PD models will be developed to address objectives that require an integrative interpretation of the study results. The pharmacokinetic model developed during part A will be used to calculated plasma concentrations and drug exposure. Clonazepam metabolism is quite variable. The model will be used to investigate whether drug exposure is related to the pharmacodynamics effects. A separate Pharmacometric Analysis Plan will be written before initiation of the PK/PD model development.

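### Section 9.9.1 provides a NONMEM model only when no linear saliva-plasma correlation is found, which conflicts with the promised model comparison and with the Part A model that section 9.9.4 relies on

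*Protocol*

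**What the plan says.** Section 9.9.1 sets up two branches for the Part A saliva and plasma data.

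- Linear branch: "When a linear correlation is found, the resulting formula will be used to estimate plasma concentrations in part B of the study".
- Other branch: "When there is no linear correlation, a population pharmacokinetic model of plasma and saliva concentrations will be constructed using nonlinear mixed effects modelling via NONMEM". The optimal model mentioned at the end of that paragraph belongs to this second branch.

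No criterion is given for when a linear correlation counts as found.

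Other parts of the protocol do not depend on a branch:

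- Section 2, repeated in the synopsis objectives, has as an objective: "To assess and compare the difference in predictive capability between linear and nonlinear (NONMEM) regression of the saliva:plasma relationship".
- The synopsis statistics paragraph says: "The predictive capability of the two regression equations will be compared to determine which method is superior". It also allows for the line failing: "In the case of a nonlinear relationship, which could be expected due to delayed penetration in the salivary compartment".
- Section 9.9.4 says population PK and PK/PD models will be developed, and: "The pharmacokinetic model developed during part A will be used to calculated plasma concentrations and drug exposure".
- The synopsis bases the PK-PD relationship on something simpler: "calculating the estimated plasma concentration using the derived formula in part A of the study".

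Section 6.2 gives one list of PK parameters for both parts (Cmax, tmax, terminal rate constant and half-life, AUC0-inf, AUC0-last, Cl, Vz) under the line "Part A: serum and saliva. Part B: saliva only". Table 2 schedules Part B saliva at 4.5 h and 5 h on Days 1 and 22, with a pre-dose sample on Day 22 only.

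**The concern.** A comparison of two methods needs both of them fitted. Section 9.9.1 treats them as alternatives, so in the linear branch the objective in section 2 has no second model, and section 9.9.4 refers to a model that 9.9.1 has not asked anyone to build.

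The gate is also the wrong kind of test. A correlation shows association. The purpose in Part B is to predict plasma concentration from saliva, and a clear correlation can coexist with poor prediction, above all when saliva lags plasma as the synopsis considers possible. The formula carried into Part B could then be the one that passed a correlation screen, with nobody having checked whether it was the better predictor.

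At stake are one stated objective and the quality of the Part B exposure estimates. Safety and the clonazepam-placebo comparison are not affected.

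**Working it through.** **Consistency check.** The protocol gives no sample-size or power figure for the saliva-plasma analysis, so there is none to reproduce. The sections can be set against each branch of 9.9.1:

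| Promise | Linear correlation found | Not found |
|---|---|---|
| Compare linear and NONMEM prediction (section 2, synopsis) | No NONMEM model provided | NONMEM model available for comparison |
| Part A PK model for exposure (9.9.4) | Not provided by 9.9.1 | Available |
| PK-PD with a derived formula (synopsis) | Possible | Possible with model predictions |

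The conflict lies in the linear branch.

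**How low the gate could be.** Inputs: Table 1 has 9 paired sampling times (0, 0.5, 1, 2, 4, 6, 8, 24 and 48 h). Part A has 10 to 20 subjects (20 in the synopsis design paragraph). Assumptions not in the protocol: a correlation counts as found at two-sided p<0.05, and pairs are independent. The critical value is r = t / √(n − 2 + t²), with t the 97.5% point on n − 2 degrees of freedom.

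- 20 × 9 = 180 pairs: 1.973 / √(178 + 3.89) = 0.146
- 10 × 9 = 90 pairs: 1.987 / √(88 + 3.95) = 0.207
- Without the 0 h pair, which coincides with a single dose: 160 pairs 0.155; 80 pairs 0.220
- Opposite extreme, one independent pair per subject: n = 20 gives 0.444; n = 10 gives 0.632

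For scale, the lower diazepam correlation cited in section 1.4.4 is 0.81. It passes every one of these, yet 1 − 0.81² = 0.34, so about a third of the variance is left unexplained. That figure is for diazepam, not clonazepam.

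**Illustration with delayed saliva.** Simulated Part A data used a one-compartment model, half-life about 30 h, 15% residual CV, 30% between-subject CV in the saliva:plasma ratio and a salivary delay half-life of 0.2 to 6.9 h (all assumed). A pooled p<0.05 test declared a linear correlation in 95-100% of trials with 20 subjects. With 10 subjects it did so in 63% at the longest delay and 99.8-100% otherwise. The direction is clear, but the size depends on these assumptions and on the p<0.05 rule.

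**Part B parameters (a separate matter).** The synopsis gives tmax 1-4 h and half-life 20-40 h.

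- No post-dose sample falls within 1-4 h, so an observed Day 1 tmax can only be 4.5 h or 5 h, and Cmax is the larger of two late values.
- Over the 0.5 h between samples, concentration falls by 1 − 2^(−0.5/40) = 0.86% to 1 − 2^(−0.5/20) = 1.72%.
- The true terminal rate is ln 2/40 = 0.017 to ln 2/20 = 0.035 per h. With an assumed measurement CV of 5-15%, a two-point slope has standard error CV × √2 / 0.5 = 0.14 to 0.42 per h, several times the quantity itself. Half-life, AUC0-inf, Cl and Vz all depend on it.

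AUC0-last is left out of this list: a trapezoid can formally be drawn, although it would skip the absorption phase.

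**The case against.** The best defence is that 9.9.1 only says which formula is carried to Part B and does not forbid a NONMEM model. Section 9.9.4 promises population PK models without condition and leaves detail to a separate Pharmacometric Analysis Plan. The study is exploratory with no primary endpoint, section 9.10 permits data-driven analyses, and the Part A pairs are collected under either branch, so the comparison could be run at any time. The linearity criterion may properly sit in an analysis plan that is not shown, and a pharmacometrician might judge it from plots or residuals.

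Much of this stands as to consequence: nothing is lost irreversibly. It does not remove the contradiction. Reading 9.9.4 as overriding 9.9.1 concedes that they disagree, and the problem is a stated rule that conflicts with an objective, which is more than missing detail.

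Three stronger readings are tempting, and the documents do not support them:

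- *The NONMEM condition is what puts the Part B PK endpoints out of reach.* Sparse sampling does that. Even in the NONMEM branch, 9.9.1 uses the model only to predict plasma concentrations, so always fitting both models would not by itself rescue the list in 6.2.
- *The PK/PD plan collapses.* In the linear branch the synopsis's concentration-effect analysis can still be run. What 9.9.1 fails to supply is the PK model for exposure.
- *A linear correlation is almost certain to be found.* This needs the assumed p<0.05 rule. Repeated samples within a subject are not independent, Part A may have only 10 subjects, and the simulated rate then fell to 63% at the longest delay.

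**Conclusion.** The contradiction is real. Whenever a linear correlation is found, section 9.9.1 as written provides no second model for the comparison promised in section 2 and the synopsis, and no Part A PK model for section 9.9.4. This rests on the text alone and needs no assumption.

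That the gate is weak follows from its nature, since correlation is not prediction. How weak depends on an unstated criterion: under p<0.05 with pairs treated as independent, r of about 0.15 to 0.21 suffices; with one independent pair per subject it would be 0.44 to 0.63.

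The Part B endpoint problem is also real, but it has a different cause and needs its own edit. The slope figures rest on an assumed CV. The absence of any post-dose sample between 1 h and 4 h does not.

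This should be corrected. It concerns one exploratory objective and the Part B exposure estimates, and the data to resolve the first part are collected in any case.

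**What to change.** In section 9.9.1, remove the condition and fit both the linear and the NONMEM model in all cases. State one measure of comparison: a subject-level cross-validated error in predicting plasma from saliva, for example leave-one-subject-out. Report it over all sampling times and also for the post-absorption times that Part B samples. Both views are needed, because the early times are where a salivary delay would most separate the models and the late times are where the chosen one will be used. Carry the better predictor into Part B. Then align 9.9.4 and the synopsis so that all three name the same source for estimated plasma concentration and exposure.

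Separately, in section 6.2 and the synopsis endpoint list, limit Cmax, tmax, the terminal rate constant, half-life, AUC0-inf, Cl and Vz to Part A. For Part B list the observed saliva concentrations (Day 1: 4.5 h and 5 h; Day 22: pre-dose, 4.5 h and 5 h) and model-predicted exposure.

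The cost is some modelling time on data already collected, a few paragraphs of wording, and fewer PK parameters promised for Part B. No extra samples are needed. Section 10.6.2 classes changes of statistical analysis as non-substantial; the sponsor would need to decide whether the edit to the endpoint list falls under that.

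### Section 9.9.1 builds the NONMEM model only if no linear saliva-plasma correlation is found, which contradicts the unconditional objective to compare linear with NONMEM prediction and does not fit the Part A model assumed in 9.9.4

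*Protocol*

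**What the plan says.** Protocol section 9.9.1 sets out two branches for the Part A saliva-plasma data:

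- Linear branch: "When a linear correlation is found, the resulting formula will be used to estimate plasma concentrations in part B of the study".
- Other branch: "When there is no linear correlation, a population pharmacokinetic model of plasma and saliva concentrations will be constructed", by nonlinear mixed effects modelling in NONMEM.

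The objective in section 2, repeated in the synopsis, carries no such condition: "To assess and compare the difference in predictive capability between linear and nonlinear (NONMEM) regression of the saliva:plasma relationship". The synopsis paragraph on sample size and statistical methodology says that both kinds of relationship will be explored, and then: "The predictive capability of the two regression equations will be compared to determine which method is superior".

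Two further statements bear on how the result is used. Section 9.9.4 says: "The pharmacokinetic model developed during part A will be used to calculated plasma concentrations and drug exposure". The synopsis says that the PK-PD relationship will be assessed "by calculating the estimated plasma concentration using the derived formula in part A of the study".

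**The concern.** A comparison of two methods needs both to be fitted. Section 9.9.1 makes the construction of the NONMEM model conditional, not merely its use in Part B. An analyst who follows that section and finds a linear correlation stops with one fitted method, and a stated objective has no answer.

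The rule for choosing the Part B method is also the wrong one for the stated purpose. The objective and the synopsis ask which method predicts plasma better. Section 9.9.1 asks only whether a linear correlation exists. These are different questions: saliva that lags behind plasma can still correlate linearly with it, so the rule could select the formula where the mixed model predicts better. The synopsis itself expects that delayed penetration into saliva could make the relationship nonlinear.

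Finally, section 9.9.4 speaks of a PK model already developed in Part A. In the linear branch, 9.9.1 does not produce one.

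**Working it through.** The protocol gives no figure to reproduce here. The check sets the sections side by side and then asks how likely the conflicting branch is.

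**1. What each section requires in each branch**

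| Section | Linear correlation found | No linear correlation |
|---|---|---|
| 9.9.1 | Linear formula only | NONMEM model built |
| Section 2 and synopsis objectives | Both methods, compared | Both methods, compared |
| Synopsis, statistical methodology | Both equations, better one identified | Both equations, better one identified |
| 9.9.4 | Uses a Part A PK model | Uses a Part A PK model |

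The requirements conflict in the left-hand column. In the right-hand column a NONMEM model exists, and the linear regression has already been tried in order to reach that branch, so a comparison is possible.

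**2. How likely is the linear branch?**

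Inputs from the protocol:
- Saliva-plasma correlations for diazepam of 0.81 and 0.96 (section 1.4.4). The same section says that no such study exists for clonazepam.
- Part A size of 20 (synopsis, study design) or 10 to 20 (synopsis, subjects).
- Eight post-dose paired samples per subject (Table 1: 0.5, 1, 2, 4, 6, 8, 24 and 48 h).

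Assumption: section 9.9.1 gives no criterion for when a linear correlation counts as found, so I take two-sided p < 0.05.

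Smallest correlation that would count: r_crit = t / sqrt(n - 2 + t²), where t is the 97.5% point on n - 2 degrees of freedom.
- n = 20: t = 2.101, so r_crit = 2.101 / sqrt(18 + 4.414) = 0.444.
- n = 10: t = 2.306, so r_crit = 2.306 / sqrt(8 + 5.318) = 0.632.
- Pooled post-dose pairs: 0.155 for 20 × 8 = 160 and 0.220 for 10 × 8 = 80. These are nominal only, because pairs repeat within subjects.

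Probability of finding it (Fisher z): Φ(atanh(r) × sqrt(n - 3) - 1.96).
- n = 20, r = 0.81: 1.127 × 4.123 - 1.96 = 2.69, giving 0.996.
- n = 20, r = 0.96: 1.946 × 4.123 - 1.96 = 6.06, giving about 1.0.

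| True r | 10 independent points | 20 independent points | 160 pooled pairs (nominal) |
|---|---|---|---|
| 0.30 | 0.13 | 0.25 | 0.97 |
| 0.50 | 0.31 | 0.62 | 1.00 |
| 0.81 | 0.85 | 0.996 | 1.00 |
| 0.96 | 0.999 | 1.00 | 1.00 |

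If clonazepam resembles diazepam, the branch in which 9.9.1 yields no NONMEM model is the expected one. Pooling the pairs would nominally find a correlation almost always, even at a true r of 0.30, which is too weak for useful prediction.

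**The case against.** The strongest reply is that the comparison is planned. The synopsis says that both relationships will be explored and compared, nothing in 9.9.1 forbids fitting both, and the study is exploratory with no primary endpoint. This stands in part. The protocol does not lack the comparison; it contains two inconsistent instructions, and the objective is lost only if 9.9.1 governs. But 9.9.1 is the section that sets out the PK analysis, so an analyst may reasonably follow it. The amendment log records that the comparison objective was added in Amendment 2; one plausible explanation, which cannot be confirmed, is that 9.9.1 was not aligned with it.

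A reader might also infer that the PK/PD analysis would have no PK model at all. The documents do not support that. Section 9.9.4 opens without condition: "Population PK and PK/PD models will be developed to address objectives that require an integrative interpretation of the study results". It leaves the detail to a separate Pharmacometric Analysis Plan, and the synopsis offers a route based on the derived formula, which the linear branch does supply. What remains is narrower: 9.9.4 refers to a Part A model that 9.9.1 does not build in the linear case.

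A reader might further blame 9.9.1 for the absence of concentrations at the 1 h and 3 h NeuroCart batteries. That gap comes from Table 2, which places Part B saliva samples at 4.5 and 5 h, plus pre-dose on Day 22. No saliva is taken at 1 h or 3 h in either branch, and any value there would be a model prediction.

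The detail of how the comparison is scored normally belongs in the SAP or the pharmacometric plan, so its absence here is not a fault. The point is a stated rule that contradicts another, not an omission.

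**Conclusion.** The contradiction holds. Section 9.9.1 makes the NONMEM fit conditional, while section 2 and the synopsis require the comparison unconditionally. If 9.9.1 is followed in the linear branch, one stated objective goes unanswered and the Part B conversion is chosen by the presence of a correlation, not by predictive performance. Section 9.9.4 also needs to be brought into line.

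The contradiction itself rests on the text alone. The view that the linear branch is likely (0.996 or more with 20 independent points, 0.85 to 0.999 with 10) rests on two assumptions: a two-sided 5% criterion, and diazepam correlations carrying over to clonazepam.

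The consequence is limited. The affected objective is a methodological one in Part A, with some effect on the exposure estimates for Part B. The clonazepam-placebo comparisons in 9.9.2, the safety analysis and the randomisation are untouched. It should be corrected, but it is not a critical defect.

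**What to change.** Reword the last paragraph of 9.9.1 along these lines:

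- Fit both the linear regression and the NONMEM model to the Part A data in every case.
- Compare them on prediction of plasma in subjects whose plasma is withheld from the fit, for example by leaving out one subject at a time. Let both methods use the withheld subject's saliva, because that is what will be available in Part B. Do not score NONMEM on typical-subject predictions with random effects set to zero: these can ignore the subject's own saliva and would handicap it against the linear formula.
- Use the better predictor for the Part B conversion.
- Retain the Part A population PK model for 9.9.4, whichever method wins.

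Then align 9.9.4 and the synopsis so that both name the same source for the Part B plasma estimates.

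The cost is one paragraph plus two short alignments. The objective already requires the NONMEM work, and the added cross-validation is a few hours of computing. Section 10.6.2 classes statistical analyses other than those described in the protocol as non-substantial changes, so the administrative burden should be small.
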